Protocol No. 2017-7706

Title: Randomized Controlled Trial Investigating Use of Liposomal Bupivacaine in Bariatric Surgery.

Study Key Name Liposomal Bupivacaine in Bariatric Surgery

Protocol No: 2017-7706

Protocol Date: 1/24/2017

[name]
Montefiore Medical Center
Department of Surgery
[name]
[name]
[contact]
email: [contact]

TABLE OF CONTENTS

Table of Contents	ii
Abbreviations and Definitions of Terms.....	iii
Abstract.....	v
1.1 INTRODUCTION	1
1.2 COMPLIANCE STATEMENT	1
1.3 RELEVANT LITERATURE AND DATA	1
2.1 PRIMARY OBJECTIVE	2
2.2 SECONDARY OBJECTIVES	2
3.1 GENERAL SCHEMA OF STUDY DESIGN.....	2
3.2 STUDY DURATION, ENROLLMENT AND NUMBER OF SITES	2
3.2.1 Date Range of Study	2
3.2.2 Total Number of Study Sites/Total Number of Subjects Projected	2
3.3 STUDY POPULATION	3
3.3.1 Inclusion Criteria	3
3.3.2 Exclusion Criteria	3
4.1 DATA VARIABLES AND SOURCES	4
4.1.1 Subject Recruitment	4
4.1.2 Data sources	4
4.2 MEASURES TO AVOID BIAS.....	4
5.1 PRIMARY AND SECONDARY OUTCOMES	4
5.2 SAMPLE SIZE AND POWER	5
5.3 DATA ANALYSIS PLAN	5
5.4 RANDOMIZATION.....	5
6.1 DATA COLLECTION AND MANAGEMENT	5
6.2 CONFIDENTIALITY	6
6.3 REGULATORY AND ETHICAL CONSIDERATIONS.....	6
6.3.1 Risk Assessment	6
6.3.2 Potential Benefits of Study Participation	6
6.3.3 Data Safety Monitoring Plan	6
6.4 INFORMED CONSENT.....	6
9.1.1 STUDY-MASTER LIST	8
9.1.2 DATA COLLECTION SHEET	9

ABBREVIATIONS AND DEFINITIONS OF TERMS

MMC	Montefiore Medical Center
LP	Liposomal Bupivacaine
LSG	Laparoscopic Sleeve Gastrectomy
LRYGB	Laparoscopic Roux en y Gastric Bypass
PCA	Patient Controlled Analgesia
TAP	Transversus Abdominis Plane
LB	Liposomal Bupivacaine
RB	Regular Bupivacaine

ABSTRACT

Context:

There has been increasing effort to reduce the use of opiates in the general population. The obese population, and in particular those undergoing bariatric surgery, represent an especially high-risk group for the adverse effects associated with opiate use.

The aim of this study is to perform a randomized controlled trial for patients undergoing bariatric surgery, comparing the need for opiates with and without administration of a transversus abdominis plane (TAP) block using the long acting local anesthetic, liposomal bupivacaine (Exparel®). From this study, we will investigate whether use of long acting local anesthetic can reduce the need for opiates in the bariatric population.

Objectives:

- To determine the effect of using long acting local anesthetic for a transversus abdominis plane block on opiate use in the bariatric population

Study Design:

- A prospective randomized controlled trial investigating the use of long acting local anesthetic for transversus abdominis block in patients undergoing bariatric surgery at Montefiore Medical Center.

Setting/Participants:

- This is a single center study of patients undergoing bariatric surgery in the Department of Surgery at Montefiore Medical Center.

Study Interventions and Measures:

- Main study outcome measures will include but not limited to: opiate use (adjusted for opioid equivalence).
- Secondary study outcome measures will include: 24-hour composite pain scores, length of stay, respiratory complications (pneumonia, atelectasis), venous thromboembolic event, myocardial infarction, nausea, vomiting, time to adequate oral intake (3 ounces each hour), and time to ambulation.

1 BACKGROUND INFORMATION AND RATIONALE

1.1 Introduction

More than one third of the population in the United States is obese. Over 190,000 people have undergone bariatric surgery each year for the last 2 years. The most common procedures performed are the laparoscopic sleeve gastrectomy (LSG) and laparoscopic roux en y gastric bypass (LRYGB). Pain management is essential for prevention of post operative respiratory complications. Obtaining adequate analgesia, particularly judicious administration of opiates, can be a double-edged sword. While opiates provide a large part of the post operative pain regimen that is essential to achieve early ambulation and accommodate adequate ventilation and chest excursion, it also acts as a respiratory depressant and holds strong addictive potential. The aim of this study is to perform a prospective randomized controlled trial of patients undergoing bariatric surgery examining opiate use and pain control in those who undergo intraoperative TAP block with liposomal bupivacaine (LB) or regular bupivacaine (RB) compared to those who receive standard postoperative pain regimens.

1.2 Compliance Statement

This study will be conducted in full accordance of all applicable Montefiore Medical Center Research Policies and Procedures and all applicable Federal and state laws and regulations including 45 CFR 46, and the HIPAA Privacy Rule. Any episode of noncompliance will be documented.

The investigators will perform the study in accordance with this protocol, will obtain consent and assent (unless a waiver is granted), and will report unexpected problems in accordance with The Montefiore Medical Center IRB Policies and Procedures and all federal requirements. Collection, recording, and reporting of data will be accurate and will ensure the privacy, health, and welfare of research subjects during and after the study.

1.3 Relevant Literature and Data

Increased opiate use is associated with increased rates of delirium, ileus, urinary retention, and respiratory depression. Transversus abdominis plane (TAP) block is a safe and effective approach to achieve optimum pain control and reduce the use of opiates in patients undergoing major abdominal surgery. A randomized controlled trial comparing TAP block with bupivacaine and a standard post-operative analgesia regimen demonstrated a reduction in visual analog pain scales throughout the initial 24 hour post-operative period, as well as a 4-fold reduction in the amount of morphine required by patients. All of the patients included in this study were undergoing exploratory laparotomy and bowel resection (McDonnell et al).

Numerous studies have compared the use of liposomal bupivacaine and non-liposomal anesthetic for the use of TAP block with data indicating a benefit with the use of liposomal bupivacaine. Fayeizadeh et al. compared TAP block in patients undergoing abdominal wall reconstruction with historical cohorts. This study demonstrated improved pain scores and decreased narcotic consumption with the TAP block. Keller et al. performed a prospective pilot study comparing pain scores and narcotic use with and without TAP block in patients undergoing colorectal surgery. They found that the group who underwent TAP block had decreased pain scores, decreased narcotic use and shorter length of stay compared with the control group. Hutchins et al. compared the use of liposomal bupivacaine with nonliposomal local anesthetic in patients undergoing hysterectomy. This trial was a prospective randomized controlled observer blinded study. It demonstrated decreased total opioid use in the first 72 hours after surgery as well as decreased pain scores.

Morbidly obese patients due to high incidence of obstructive sleep apnea (OSA) are predisposed to opioid induced airway obstruction and thus frontline high ceiling analgesics (opioids) have concerns based on safety in their liberal use (Alvarez et al). Multiple studies have demonstrated a decrease in post-operative pain and thus diminished opioid consumption post-intervention. The morbidly obese bariatric population, who are at a particularly higher-risk for opioid induced complications such as apneic events and possible cardiac death, would benefit from a post-surgical analgesia regimen that would decrease or eliminate said risks.

2 STUDY OBJECTIVES

- The aim of this study is to perform a prospective randomized controlled trial to investigate the effect of performing a TAP block using long acting local anesthetic on opiate use and pain control in the bariatric population. From this data we propose to determine if we can adequately and safely forego implementation of PCA and reduce the overall use of opiates, while providing sufficient analgesia.

2.1 Primary Objective

- To determine if the use of long acting or regular acting local anesthetic for TAP block will have an effect on the use of opiates in patients undergoing bariatric surgery at MMC.

2.2 Secondary Objectives

- To identify associations between demographic factors, such as age, race, types, pathology findings with outcomes.
- To identify any difference in 24 and 48-hour composite pain scores, the length of stay, incidence of cardiac or respiratory complications, or incidence of venous thromboembolic events between the three groups.

3 INVESTIGATIONAL PLAN

3.1 General Schema of Study Design

- Prospective randomized controlled trial of patients undergoing bariatric surgery at Montefiore Medical Center.
- This will only include inpatient data

3.2 Study Duration, Enrollment and Number of Sites

3.2.1 Date Range of Study

- Cases included will take place at MMC between 01/01/2018 and 12/31/2018 over a 1 year period.

3.2.2 Total Number of Study Sites/Total Number of Subjects Projected

- This prospective study will enroll patients at a single study site of MMC (Moses Division).
- We plan to enroll 219 patients/subjects (73 patients for each arm)

3.3 Study Population

3.3.1 Inclusion Criteria

- 1) Obese patients undergoing bariatric surgery (LSG or LRYGB)
- 2) Patients 18 years of age and older
- 3) Surgical treatment between 01/01/2018 and 12/31/2018 over a 1 year period

3.3.2 Exclusion Criteria

- 1) Patients under the age of 18 years old
- 2) Patients taking any opiates within 30 days of enrollment in the trial
- 3) Patients with a history of chronic pain.
- 4) Patients taking pregabalin or gabapentin.
- 5) ASA IV
- 6) Prior laparotomy
- 7) Body Mass Index $\geq 60 \text{ kg/m}^2$
- 8) History of cardiac arrhythmia
- 9) History of Seizure
- 10) Psychiatric Diagnosis currently on antipsychotic medication
- 11) Pregnancy
- 12) Patients who are breastfeeding.

4 STUDY PROCEDURES

Patients will be randomized to either receive an intraoperative TAP block with LB, an intraoperative TAP block with RB, or no TAP block. All patients will receive standard post-operative analgesia regimen. This includes fentanyl PCA at 10mcg every 10 minutes for the first 24 hours. Acetaminophen with codeine elixir (360mg/36mg) by mouth every 4 hours, ketorolac 30mg intravenously every 6 hours and dilaudid 0.4mg intravenously every 3 hours are for breakthrough pain are ordered post- postoperatively and continued until discharge.

The solution used to perform the TAP block with LB will comprise of 20mL of liposomal bupivacaine solution, 30mL of 0.25% bupivacaine, and 100mL of normal saline. The solution used to perform the TAP block with RB will comprise of 50mL of 0.25% bupivacaine and 100mL of normal saline. The TAP block is performed under laparoscopic visualization. An initial 5mm optical trocar is placed. The peritoneum and then TAP are then infiltrated with the local anesthetic under direct visualization. Skin incisions are infiltrated and trocar sites are anesthetized prior to placement of ports. Analog pain scale will be used to determine the pain score of the subjects as they emerge from general anesthesia (Time 0 hours). Pain scores will be recorded every 4-6 hours

by the nursing staff as reported by the patients. Patients will be monitored for secondary post-operative complications up to the 2-week mark following intervention.

4.1 Data Variables and Sources

4.1.1 Subject Recruitment

All subjects will have undergone the standard rigorous preoperative evaluation by our multidisciplinary team. Risks and benefits will be explained to subjects in our clinic and consent will be obtained by our research coordinator during the preoperative visit.

4.1.2 Data sources

The subject will be the primary source of demographic data and past medical history. The electronic medical record will also be reviewed prior to offering enrollment to ensure that patients meet all of the inclusion criteria and do not meet any of the exclusion criteria. Pain scores and quantity of opiates used will be documented by nursing staff.

4.2 Measures to Avoid Bias

All patients enrolled in the study will be blinded. The TAP block is performed intraoperatively, and there is no outward sign of injection that would allow the patient or person examining the patient to tell whether the patient had received the TAP block. The surgeon will not be blinded. The liposomal bupivacaine has a distinct cloudy appearance that would be difficult to replicate otherwise. In addition, as part of the TAP block, the transversus abdominus plane is hydrodissected by the local anesthetic. Injection/hydrodissection using a placebo (no local anesthetic) may increase pain and therefore has been excluded from the control arm of the study. Anesthesia will be blinded. The anesthesiologist will leave the room and be replaced by another anesthesiologist for the duration of the block. Once an appropriate amount of time has lapsed, the attending anesthesiologist will return to the room. This is done so as to avoid bias in administration of opiates intraoperatively by anesthesia depending on which arm of the study the patient is on. In addition, the nursing staff will be blinded, which is important as they will be recording the pain scores as per nursing protocol. The research staff collecting data will not be blinded. Pharmacy will document in the orders "Study Drug – TAP Block." This will allow researchers to look through the record and know the patient was enrolled in the study, but it will not allow them to know which arm of the study the patient was in.

All relevant chart information and collection will be standardized to avoid bias. Before commencing chart reviews, all relevant terminology will be determined and standardized. The specific sources of relevant information will be identified, as will their location within the documents. During the review process, regular meetings between the Principal Investigator and chart reviewer will be held to discuss any modifications to the standard that may be needed. Five percent of charts will be selected at random and reviewed by a third party who is trained in the standardized terminology and sources of information in order to validate the original review for accuracy.

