5 STATISTICAL CONSIDERATIONS

5.1 Primary and Secondary Outcomes

The primary outcome will be quantity of opiates used in terms of morphine equivalents. Secondary outcomes will include 24-hour composite pain scores, length of stay, respiratory

complications (pneumonia, atelectasis), venous thromboembolic event, myocardial infarction, nausea, vomiting, time to adequate oral intake (3 ounces each hour), and time to ambulation. Pain scores will be recorded by nursing staff using the universal pain assessment tool.

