5.4 Randomization

The research data collector will be responsible for the randomization. Subjects will be randomized in a 1:1:1 ratio to receive LB as a TAP block infiltration or RB as a TAP block infiltration or no TAP block infiltration.

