9 APPENDIX

9.1.1 STUDY-MASTER LIST

Study number	Patient's name	Patient's medical record number	Operative Procedure	24-Hour Composite Pain Score	Overall Opioid Use in morphine equivalents
1					
2					
3					
4					
5					

9.1.2 DATA COLLECTION SHEET**Patient study number** _____**Patient gender:** male / female**Race:** Caucasian____, African American____, Asian____, Hispanic (white)____ Other____**Patient's age** _____**Patient's weight /BMI** _____**Procedure** _____**Comorbidities** _____**Pathology** _____**Outcomes:**

Overall narcotic use _____

24-Hour composite pain score _____

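### The role that collects the primary opioid data also performs the randomization, and nothing requires opioid doses to be abstracted and converted blind to arm

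*Combined protocol and SAP*

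**What the plan says.** All references are to the combined protocol and SAP.

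- **Primary outcome.** Section 5.1: "The primary outcome will be quantity of opiates used in terms of morphine equivalents". Sections 5.2 and 5.3 set the window at 48 hours. Under section 4 the regimen includes intravenous fentanyl by PCA, oral codeine and intravenous hydromorphone, so the analyzed value is a converted sum over three drugs and two routes.
- **Source recording.** Section 4.1.2: "Pain scores and quantity of opiates used will be documented by nursing staff". Section 4.2 says that the nursing staff are blinded.
- **Data collectors.** Section 4.2: "The research staff collecting data will not be blinded". The same paragraph then describes a neutral pharmacy order label and says that "it will not allow them to know which arm of the study the patient was in".
- **Randomization.** Section 5.4: "The research data collector will be responsible for the randomization". It describes no concealment step and no separate unblinded role.
- **Chart review.** Section 4.2 fixes terminology and sources beforehand, but during review "regular meetings between the Principal Investigator and chart reviewer will be held to discuss any modifications to the standard that may be needed". It also provides a check: "Five percent of charts will be selected at random and reviewed by a third party". Neither the chart reviewer nor the third party is stated to be blinded.

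**The concern.** The plan takes trouble to protect this endpoint at the bedside. Patients and nurses are blinded, and the anesthesiologist is replaced during the block so that intraoperative opioid dosing is not influenced by arm. Those measures protect the doses given and recorded.

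The analyzed number is made later. Someone reads the record, decides which doses fall within 48 hours, adds three opioids together and expresses them as morphine equivalents. Some of those steps need judgment. If the person making them knows the arm, the judgments can differ by arm, and such a difference would appear as a treatment effect. The plan describes the data collectors as unblinded and gives one of them the allocation, so this route is left open when it could be closed cheaply.

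**Working it through.** **1. Who can know the arm at the abstraction step**

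| Text | What it implies |
|---|---|
| 4.2, statement on data collectors | Not blinded |
| 4.2, pharmacy label | The record does not reveal the arm to a researcher |
| 5.4 | The research data collector performs the randomization |
| 4.1.2 and 4.2 | Blinded nurses document the source doses |
| Any section | No requirement that abstraction or conversion be blind |

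The first two rows conflict. Section 5.4 means that the conflict cannot be settled by the label alone: the label masks the chart, not the person who allocated the patient. So the plan does not ensure blind abstraction. It also does not establish that the abstractor knows the arm, because no section says that the chart reviewer and the randomizer are the same person.

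**2. The plan's own scale, for context**

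Inputs from 5.2: mean 23.3 mg, SD 14 mg, 30% reduction, two-sided alpha 0.05, power 80%.

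- Difference: 0.30 × 23.3 = 6.99 mg.
- Per arm: 2 × (1.96 + 0.842)² × 14² / 6.99² = 63.
- Divided by the rank-test efficiency 3/π = 0.955: 66 per arm, or 198 in total, close to the stated 200. Then 66 × 1.1 = 72.6, so 73 per arm and 219 in total, as stated.

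The plan does not mention the rank-test adjustment. It is simply the variant that reproduces the stated figures, and the point does not depend on it.

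**3. What an arm-related shift would do (what-if only)**

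Assume no true effect, SD 14, 67 per arm (200/3), and one arm's mean shifted by a fraction b of 23.3 mg. For the three-group ANOVA the noncentrality is λ = n × d² × (2/3) / SD², with d = b × 23.3. The critical value is F(0.95; 2, 198) = 3.04.

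| Assumed b | d (mg) | λ | Rejection probability |
|---|---|---|---|
| 0 | 0 | 0 | 5.0% |
| 5% | 1.17 | 0.31 | 7.4% |
| 10% | 2.33 | 1.24 | 15.2% |
| 15% | 3.50 | 2.78 | 29.7% |
| 20% | 4.66 | 4.95 | 49.3% |

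A gamma simulation of the 5% and 10% rows gave 7.6% and 15.7% for ANOVA, and 7.0% and 14.8% for Kruskal-Wallis. The documents give no estimate of b, and b may be zero.

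**4. What a change unrelated to arm would do**

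Assume that 25% or 50% of charts, chosen without regard to arm, are converted on a scale 1.25 to 3 times higher. With three arms of 67 and no true effect, simulated type I error stays at 4.7% to 5.0% (ANOVA) and 5.0% to 5.2% (Kruskal-Wallis). A neutral inconsistency therefore does not create false positives. Its cost is power: for control against a 30% reduction with SD 14 in both arms, two-sample t-test power falls from 81% to about 80% at ratio 1.25. Larger losses need ratios that nothing in the documents suggests.

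**5. What the second review can catch**

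0.05 × 219 = 10.95, so 11 charts. The hypergeometric probability that none of the 11 is an affected chart is:

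| Affected charts of 219 | P(none sampled) |
|---|---|
| 7 | 69% |
| 22 | 30% |
| 55 | 4% |
| 110 | 0.04% |

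The check would probably sample a widespread problem and would often miss a small one. Section 4.2 describes it in terms of terminology and sources and does not say that it covers conversion.

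**The case against.** The case on the other side is substantial.

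- **The key sentence is contradicted a few lines later.** A label designed to hide the arm makes little sense if collectors are meant to know it, so the unblinded statement may be loose drafting. This stands in part: the text needs reconciling. But 5.4 gives the allocation to the data collector whichever sentence was intended.
- **The source doses are protected.** Blinded nurses document them and they stay in the record, so a blind re-derivation remains possible. This stands, and it limits the risk.
- **The study's own files offer some masking.** Neither appendix form has an arm field, and 6.1 replaces identifiers with surrogate numbers for analysis. This is true, but neither measure removes knowledge of the arm from someone who randomized the patient.
- **The bias figures rest on assumptions.** No section provides for arm-dependent conversion. This stands in full: the figures show sensitivity, not expected harm.

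A reader might also infer that the opioid total cannot be audited, because the data collection sheet (9.1.2) has only the field "Overall narcotic use" and no conversion table is given. The documents do not support that. The sheet also omits most of the listed secondary outcomes, so it is plainly not the full data set, and 6.1 refers to spreadsheets whose fields are not shown. The absent table and dose fields are missing detail, not evidence of a design flaw.

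**Conclusion.** The point holds as an avoidable risk. The plan places knowledge of the allocation in the data-collecting role and does not require the primary outcome to be abstracted and converted blind to arm. It contradicts itself on whether researchers can know the arm, and it allows the abstraction standard to change without requiring that changes be decided blind or applied to charts already reviewed.

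A reader might go further and conclude that the primary result will be biased, that one person both randomizes and reviews charts, or that conversion factors will be altered during review. None of these is supported. No section identifies the chart reviewer with the randomizer, and the standard that may be modified is described as terminology and sources, without mention of conversion.

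The actual size is unknown. The 7.4% and 15.2% type I error figures hold only under assumed one-arm shifts of 5% and 10%. The unblinded statement and the assignment of randomization are explicit text, not inference. The change is worth making because it closes the route at little cost, not because harm has been shown.

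**What to change.** 1. **Section 5.4:** assign generation and holding of the allocation list to someone who does not abstract outcomes. Pharmacy is a natural candidate because it already labels the study drug. The plan does not say whether pharmacy handles patients in the no-block arm; if it does not, use another existing staff member.
2. **Section 4.2:** replace the statement that data collectors are unblinded with a requirement that whoever abstracts and converts opioid doses has no access to arm. This also resolves the conflict with the label sentence.
3. **Section 4.2:** require that any change to the abstraction standard during review be decided blind to arm and applied to all charts, including those already reviewed.

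The cost is a small reassignment of existing roles, plus re-abstraction if the standard does change. Treatment, visits and sample size stay as they are. A pre-specified conversion table and fields for drug, dose, route and time would be useful additions, but the point does not depend on them.
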